Intent-to-Treat (ITT) Population: This population will comprise all randomised subjects, excluding those who were randomised in error. A subject who is recorded as a screen failure, run-in failure, or stabilisation failure, but is randomised and does not receive a dose of study treatment, is considered to be randomised in error. Any other subject who receives a randomisation number will be considered to have been randomised. This will constitute the primary population for all ~~efficacy and safety~~ and pharmacodynamic analyses.

Section 9.3.2: Interim Analysis

Rationale for change: Refer to rationale stated for Sections 4.3 and 5.4.1.

An interim analysis is planned after ~~15-10~~ subjects have completed the following critical assessments:

- PASP at T0 and T3 for both study periods
- Oxygen saturation at T0 and T3 for both study periods
- Adverse events

The interim analysis will use the following study data:

- PASP at time T0 and T3 for both periods, for the first ~~15-10~~ subjects

- Oxygen saturation at T0 and T3 for both periods, for the first 15-10 subjects
- Adverse events for the first 15-10 subjects
- ~~Angiotensin biomarker~~RAS peptide concentrations for the first 5 subjects (to allow time for the samples to be analysed by the external lab).

The interim analysis will use a data snapshot that has been cleaned to the best extent allowed by the timeframes (i.e. the interim data will not be fully cleaned or fully QC'd data and there will not be a locked database).

The aims of the interim analysis, and the endpoints to be used to address them, are as follows:

- Using the primary endpoint (treatment differences between GSK2586881 and Placebo in change from pre-dose PASP to hypoxic/exercised PASP [T3-T0]):
 - To decide whether to continue the study or stop based on futility, and
 - to conduct an advisory sample-size re-estimation with the view to potentially reduce the number of subjects participating in the study below 3020.
- Using secondary endpoints:

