Approximately 35 subjects will be enrolled to ensure that a minimum of 30 subjects complete all dosing and critical assessments (the target of 30 may be revised by the sample size re-estimation).

If subjects prematurely discontinue the study, additional replacement subjects will not be recruited in order to preserve randomisation integrity.

Analysis

This study is designed to estimate the effect of GSK2586881 relative to placebo on change from baseline in PASP following exercise under hypoxic conditions. No formal hypothesis will be tested. Point estimates will be calculated together with corresponding 95% confidence intervals (or credible intervals if utilising a Bayesian framework) for the difference between the mean of the test treatment and the mean of the reference treatment.

Analysis of PASP: Statistical modelling of changes from baseline (Ti-T0) will be done using a Bayesian mixed effects regression model, including covariates for period, treatment, period baseline and subject baseline (the mean of the two period baselines) as fixed effects and subject as a random effect. A compound symmetric covariance structure within each subject-period-treatment cell will be assumed to account for repeated measurements a) inherent in the two-period crossover design and b) due to the four post-baseline timepoints within each treatment period. Non-informative priors will be used for the model parameters. Posterior distributions will be obtained for the GSK2586881 Vs Placebo comparisons at each of the post dosing timepoints (T1-T4). These distributions will be used to produce several posterior probability statements; the most important being the probability that the change from baseline in PASP is reduced by the GSK2586881 at time T3.

[figure not shown]
Oxygenation saturation will also be analysed in a similar way; although of interest is the posterior probability that the study drug causes (absolute) reductions in oxygenation saturation in excess of 5%.

An interim analysis is planned after 15 subjects have completed period 1 and 2 assessments to i) evaluate safety and tolerability (SAE, AE and Oxygenation saturation), ii) determine whether the study should stop for futility based on expected PASP outcomes if the study were allowed to complete recruitment and iii) Re-estimate the sample size based using the observed variance parameters.

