5.4.1. Study Stopping Criteria

An interim analysis is planned after approximately 15 subjects have completed treatment periods 1 and 2 and the study may be stopped if a reasonable change in PASP is not observed after dosing with GSK 2586881 or if review of the safety data suggests a change in the benefit-risk profile. The decision to stop the study will be made by the core members of the GSK study team.

Safety data that is collected on a continuous basis (oxygen saturation and telemetry) will be monitored live on site to determine whether a subject tolerates the hypoxia/exercise challenge; study procedures may be aborted on safety grounds if, in the Investigator's opinion, any of these measurements reach unsafe levels. The simulated altitude within the chamber may be reduced if too many participants fail to tolerate the challenge, and the study may be stopped if participants fail to tolerate the challenge at the minimum altitude. The full criteria for this procedure (which may lead to the study being stopped) are described in Section 7.3.

In addition, the study may be stopped at the interim analysis for a safety signal in oxygen saturation under hypoxia and exercise, combined with a lack of evidence of mechanistic effect on Angiotensin biomarkers (Ang II, Ang 1-7 and Ang 1-5). Full details on stopping criteria are described together with the full procedure for the interim analysis in Section 9.3.2.

[figure not shown]

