Ventilatory parameters	X		X		X	X ¹				X	Measurements to be taken at the same time as the Echocardiograms. During the exercise challenge, an ECG integrated with the ventilatory assessment will be carried out.
Pulse Oximetry (O ₂ saturation)		←-----→									Will be continuously monitored for safety. Measurement should be recorded at time of each echocardiogram post-treatment and databased.
RAS Biomarkers	X	X ²	X ³	X ⁴		X ³		X ³	X ⁵	X ³	
Other Biomarkers	X	X ²	X ³	X ⁴		X ³		X ³	X ⁵	X ³	
PK sampling	X	X ²	X ³	X ⁴		X ³		X ³	X ⁵	X ³	

Procedure	Treatment Period 1 and 2 (Washout 3-14 days)										Notes
	Times relative to dosing				Hypoxia (Times relative to entry to Chamber)						
	Predose	0h	15 m	15-45m	0-60m	60m	60-70m	Immediately after exercise	30m rest on exit from chamber	After 30 mins rest	
AE/SAE review		←=====→									
Concomitant medication review	X										

1. To be taken at the end of exercise
2. Take at the end of the infusion
3. Taken immediately after echocardiogram
4. Immediately before entering the chamber
5. To be taken as soon as possible after leaving chamber

After written informed consent, screening assessments will be performed as outlined in the Time and Events Table (Section 7.1).

The following demographic parameters will be captured: year of birth, sex, race and ethnicity.

Medical/medication/family history will be assessed as related to the inclusion/exclusion criteria listed in Section 5.

Cardiovascular medical history/risk factors (as detailed in the CRF) will be assessed at screening.

Cardiorespiratory fitness during bicycle exercise and hypoxia tolerance will be assessed.

Procedures conducted as part of the subject's routine clinical management (e.g. blood count) and obtained prior to signing of informed consent may be utilized for Screening or baseline purposes provided the procedure meets the protocol-defined criteria and has been performed in the timeframe of the study.

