9.3.2. Interim Analysis

An interim analysis is planned after 15 subjects have completed the following critical assessments:

- PASP at T0 and T3 for both study periods
- Oxygen saturation at T0 and T3 for both study periods
- Adverse events

The interim analysis will use the following study data:

- PASP at time T0 and T3 for both periods, for the first 15 subjects
- Oxygen saturation at T0 and T3 for both periods, for the first 15 subjects
- Adverse events for the first 15 subjects
- Angiotensin biomarker concentrations for the first 5 subjects (to allow time for the samples to be analysed by the external lab).

The interim analysis will use a data snapshot that has been cleaned to the best extent allowed by the timeframes (i.e. the interim data will not be fully cleaned or fully QC'd data and there will not be a locked database).

The aims of the interim analysis, and the endpoints to be used to address them, are as follows:

- Using the primary endpoint (treatment differences between GSK2586881 and Placebo in change from pre-dose PASP to hypoxic/exercised PASP [T3-T0]):
 - To decide whether to continue the study or stop based on futility, and
 - to conduct an advisory sample-size re-estimation with the view to potentially reduce the number of subjects participating in the study below 30.
- Using secondary endpoints:
 - to estimate treatment differences between GSK2586881 and Placebo in change from pre-dose oxygen saturation to hypoxic/exercised oxygen saturation [T3-T0], with a view to stopping the study if there is evidence that GSK2586881 causes a reduction in oxygen saturation in healthy volunteers. As a non-binding guide high posterior probability of observing $\geq 5\%$ absolute differences in **mean** oxygenation saturation values between placebo and active arms would be of concern; but clinical judgement

would override any statistical methods if, for example, the majority of subjects displayed consistent patterns of reductions e.g. between 2-3%).

- to compare adverse events within the two treatment groups and explore any potential safety signals that may emerge

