9.4. Key Elements of Analysis Plan

Each subject will undergo two treatment periods in this crossover study, each one of which being subdivided into five sub-epochs (labelled T0-T4) as follows:

- T0: Pre-dose (period baseline)
- T1: Post-dose, normoxic, at rest, pre-challenge
- T2: Hypoxic, at rest
- T3: Hypoxic, immediately after exercise
- T4: Post-challenge, normoxic, at rest

This follows the principle illustrated in the diagram of echocardiograph measurements ([Figure 2](#)).

Pharmacodynamic endpoints will be assigned to T0 thru T4 timepoints based on when they happened relative to the sequence of events that the subject undertakes during the course of the study day.

Pharmacokinetic endpoints will be timed based on elapsed time since dose administration.

In addition to T0 being defined as the period baseline, an overall subject baseline will be defined as the mean of the two T0 measurements (one from each period).

Change from baseline at time points T1 - T4 will be calculated as the difference between the measurement at the time point in question and the period baseline. In general, statistical modelling of changes from baseline will be done using a Bayesian mixed effects regression model, including covariates for period, treatment, period baseline and subject baseline (the mean of the two period baselines) as fixed effects and subject as a random effect (non-informative priors for model parameters). A compound symmetric covariance structure within each subject-period-treatment cell will be assumed to account for repeated measurements a) inherent in the two-period crossover design and b) due to the four post-baseline timepoints within each treatment period.

PASP data will be summarized by treatment and time-point in tabular and graphical format. A Bayesian mixed effects regression model (as described above) will be fitted (using non-informative priors for the model parameters), and an estimate of the mean change from baseline in PASP for each treatment group and post-baseline timepoint,

together with its 95% credible interval, will be obtained. Estimates for treatment differences will also be presented. Data may be log-transformed if necessary.

Details of the analysis of other endpoints will be described in the RAP.

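### The interim drug-versus-placebo saturation comparison uses T3-T0 only, although the resting-hypoxia (T2) saturation is already databased and analysed at the end of the study

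*Protocol*

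**What the plan says.** Section 9.3.2 states which data the interim analysis will use. For saturation this is "Oxygen saturation at T0 and T3 for both periods, for the first 15 subjects". The list also holds PASP at T0 and T3, adverse events, and angiotensin peptides from the first five subjects. The saturation aim is to estimate the treatment difference in "change from pre-dose oxygen saturation to hypoxic/exercised oxygen saturation [T3-T0], with a view to stopping the study" if the drug appears to lower saturation. The size criterion begins "As a non-binding guide high posterior probability of observing" and refers to a mean difference of 5 points or more. A further clause lets clinical judgement override it, for example if most subjects show consistent falls of 2 to 3 points.

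Appendix 6, in the Amendment 02 changes to Section 9.3.2, gives the line as "Oxygen saturation at T0 and T3 for both periods, for the first 15-10 subjects" (marked-up text: 15 replaced by 10). The timepoints do not change.

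Section 9.4 defines "T2: Hypoxic, at rest" as one of five timepoints. The pulse oximetry note in the Section 7.1 treatment-period table says "Measurement should be recorded at time of each echocardiogram post-treatment and databased", which covers T2. The synopsis describes the PASP model, with comparisons at T1 to T4, and then says "Oxygenation saturation will also be analysed in a similar way".

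Section 5.4.1 allows a stop at the interim for a saturation signal in the combined hypoxia-and-exercise state together with no evidence of a biomarker effect. It also allows one "or if review of the safety data suggests a change in the benefit-risk profile", and it refers to Section 9.3.2 for the full stopping criteria.

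**The concern.** Section 2.1 explains why saturation matters here: blunting hypoxic pulmonary vasoconstriction may worsen ventilation-perfusion matching and so oxygenation. T2 is the in-chamber reading without exercise. T3 adds exercise, which the same section says brings in diffusion limitation as a further contributor. The interim therefore uses one of the two in-chamber saturation timepoints and omits the one taken under hypoxia alone.

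Two kinds of resting fall are then lost to the interim comparison. One is a fall present at T2 but not at T3. The other occurs in a subject who is withdrawn before T3: Section 9.3.2 counts subjects who have T0 and T3 in both periods, so that subject contributes no T3-T0 contrast. The interim is the planned point for comparing saturation by treatment before the remaining volunteers are dosed, and the T2 readings are already in hand.

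**Working it through.** **Passages side by side**

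| Item | Interim (9.3.2) | Collected or analysed at the end |
|---|---|---|
| T0 saturation | used | period baseline |
| T2 saturation (hypoxia, rest) | not listed | databased (7.1); analysed like PASP (synopsis) |
| T3 saturation (hypoxia, after exercise) | used; the stop contrast | databased (7.1); analysed like PASP (synopsis) |

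The rules outside the interim were checked as possible substitutes. Section 5.4 lists saturation below 65% at any point of the challenge as a ground for withdrawal. Section 7.3 lowers the altitude when three or more subjects do not tolerate the challenge. Section 5.4.1 allows a study stop for intolerance at the minimum altitude. All three cover the resting hour. All three are absolute thresholds or tolerance counts applied at a blinded site, and none estimates a drug-placebo difference.

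**Illustration of size.** The protocol states no figure to reproduce and gives no saturation SD.

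- From the protocol: n = 15 (10 after Amendment 02); guide of a 5-point mean difference.
- Assumed: SD of the within-subject drug-placebo difference s = 2, 4 or 6 points; flat prior; "high" posterior probability read leniently as above 0.5, because the protocol gives no cut-off.

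With a flat prior the posterior for the mean fall is a t distribution centred on the observed mean. P(fall ≥ 5) exceeds 0.5 exactly when the observed mean fall exceeds 5. For a true mean fall d,

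P(flag) = Φ((d − 5) / (s/√n)).

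For n = 15, s = 4, d = 6: s/√n = 4/3.873 = 1.033, (6 − 5)/1.033 = 0.968, Φ = 83%.

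| True fall at the reading used | s = 2 | s = 4 | s = 6 |
|---|---|---|---|
| 6 points, n = 15 | 97% | 83% | 74% |
| 3 points, n = 15 | <0.01% | 2.6% | 9.8% |
| 0 points, n = 15 | ~0% | ~0% | 0.06% |
| 6 points, n = 10 | 94% | 79% | 70% |
| 3 points, n = 10 | 0.08% | 5.7% | 15% |
| 0 points, n = 10 | ~0% | <0.01% | 0.4% |

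The n = 15 rows agree with 20,000 simulated interims per scenario (97%, 83%, 74% for 6 points).

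Reading the table:

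- Fall of 6 points at T2, none at T3: flagged in 74% to 97% of interims from T2, and in at most 0.06% from T3 (n = 15).
- Fall of 6 points at T2, 3 left at T3: T3 flags it in 0% to 10%.
- Fall of 6 points at both: at equal SD, T3 flags it as often as T2.
- Fall of 2 to 3 points at T2: seldom flagged from T2 either, because the guide is set at 5 points. The 3-point figures are in the table; a 2-point fall is flagged less often.

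**Cost in false alarms.** With no drug effect, using two readings at most doubles the chance of a flag. At s = 6 this is from 0.06% to at most 0.12% (n = 15), or from 0.4% to at most 0.8% (n = 10).

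**The case against.** The strongest reply is that T3 is a reasoned choice. Section 2.1 reports more desaturation under exercise plus hypoxia than under either alone, the primary objective concerns exercise in hypoxia, and Section 5.4.1 words the saturation signal in the same way. Nothing in the protocol says that exercise would mask a resting fall, and a fall that persists is already in the T3 data. This stands, and it is why T3-T0 should remain the main contrast. It does not explain leaving out a reading that is in hand and would be a second look.

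It can also be said that the interim is exploratory and non-binding, that the general safety clause in Section 5.4.1 names no timepoint, and that interim details are left to the analysis plan. Nothing bars a look at T2. But Section 5.4.1 sends the reader to Section 9.3.2, where the data list and the contrast are already fixed without it.

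Three stronger readings are tempting and not supported:

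- **That the resting part of the chamber exposure is unwatched.** Saturation is monitored live throughout. T2 is also a single reading late in the resting hour, so adding it would not cover that hour.
- **That adding T2 would catch small falls much better than T3.** This needs a rule on the probability of any fall exceeding 0.95, which Section 9.1 uses for PASP success and not for saturation, and an assumed larger SD at T3. Under the 5-point guide, falls of 2 to 3 points are left mainly to the clinical-judgement clause.
- **That vital signs and ECG are missing from the interim safety review.** Clinically significant abnormalities of either are adverse events under Appendix 4, and adverse events are on the interim list. Further tables are ordinary analysis-plan content.

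**Conclusion.** The point holds as a limited gap in the interim data set. A resting-hypoxia fall that does not persist after exercise, or that occurs in someone withdrawn before T3, cannot inform the saturation stop as Section 9.3.2 is written, and Amendment 02 leaves this unchanged. The gap is widest for a fall above the 5-point guide at rest that disappears by T3: flagged in about 74% to 97% of interims from T2 and practically never from T3 (n = 15; 70% to 94% and at most 0.4% with n = 10). If the fall persists fully, T2 adds no detection at equal SD. These figures rest on assumed SDs of 2 to 6 points and an assumed cut-off of 0.5. The protocol gives neither, and it does not say how likely a purely resting fall is.

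Sections 5.4.1 and 9.3.2 also differ. The first ties the saturation stop to the combined hypoxia-and-exercise state and to absence of a biomarker effect; the second states no biomarker condition. The two must be reconciled.

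**What to change.** In Section 9.3.2, change the interim saturation data to T0, T2 and T3 for both periods, and include T2 values from subjects who have no T3 value. Present the T2-T0 drug-placebo difference beside T3-T0, with individual subject patterns, under the existing non-binding guide and clinical-judgement clause. Keep T3-T0 as the main contrast. State in Sections 5.4.1 and 9.3.2, in the same terms, which saturation data and which conditions apply to the saturation stop.

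The cost is one changed line, one more estimate and one display, with no new measurement. The chance of a false alarm rises slightly under a guide that binds nobody. One limit remains: a subject withdrawn before the T2 echocardiogram has neither reading, and a subject with T2 in one period only gives no within-subject difference.

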9.3.3. Multiple Comparisons and Multiplicity

As this is an early-phase exploratory study, no adjustment for multiple comparisons will be made. Treatment comparisons will be presented as effect sizes with 95% confidence intervals.

9.4. Key Elements of Analysis Plan

Each subject will undergo two treatment periods in this crossover study, each one of which being subdivided into five sub-epochs (labelled T0-T4) as follows:

- T0: Pre-dose (period baseline)
- T1: Post-dose, normoxic, at rest, pre-challenge
- T2: Hypoxic, at rest
- T3: Hypoxic, immediately after exercise
- T4: Post-challenge, normoxic, at rest

This follows the principle illustrated in the diagram of echocardiograph measurements ([Figure 2](#)).

Pharmacodynamic endpoints will be assigned to T0 thru T4 timepoints based on when they happened relative to the sequence of events that the subject undertakes during the course of the study day.

Pharmacokinetic endpoints will be timed based on elapsed time since dose administration.

In addition to T0 being defined as the period baseline, an overall subject baseline will be defined as the mean of the two T0 measurements (one from each period).

Change from baseline at time points T1 - T4 will be calculated as the difference between the measurement at the time point in question and the period baseline. In general, statistical modelling of changes from baseline will be done using a Bayesian mixed effects regression model, including covariates for period, treatment, period baseline and subject baseline (the mean of the two period baselines) as fixed effects and subject as a random effect (non-informative priors for model parameters). A compound symmetric covariance structure within each subject-period-treatment cell will be assumed to account for repeated measurements a) inherent in the two-period crossover design and b) due to the four post-baseline timepoints within each treatment period.

PASP data will be summarized by treatment and time-point in tabular and graphical format. A Bayesian mixed effects regression model (as described above) will be fitted (using non-informative priors for the model parameters), and an estimate of the mean change from baseline in PASP for each treatment group and post-baseline timepoint,

together with its 95% credible interval, will be obtained. Estimates for treatment differences will also be presented. Data may be log-transformed if necessary.

Details of the analysis of other endpoints will be described in the RAP.

9.4.1. Pharmacokinetic Analyses

Pharmacokinetic analysis will be performed by, or under the auspices, of Clinical Pharmacology Modelling and Simulation Department with GlaxoSmithKline. Plasma GSK2586881 concentration-time data will be analysed by non-compartmental methods with WinNonLin V6.3 or greater. Calculations will be based on the actual sampling times recorded during the study.

From the plasma concentration-time data, the following pharmacokinetic parameters will be determined, as data permit: maximum observed plasma concentration (Cmax), time to Cmax (tmax), area under the plasma concentration-time curve over the study period [nominally AUC(0-2.5h) post-dose], AUC over the hypoxia challenge (nominally AUC(0.5-2.0h post-dose), plasma clearance (CL), volume of distribution (V) and apparent terminal phase half-life (t1/2), if data permit. Other PK parameters may also be determined.

Pharmacokinetic data will be presented in graphical and/or tabular form and will be summarized descriptively. All pharmacokinetic data will be stored in the Archives, GlaxoSmithKline Pharmaceuticals, R&D.

The relationship between the RAS biomarkers and other pharmacodynamic endpoints (echocardiography and pulse oximetry) and GSK2586881 concentrations and/or PK parameters may also be explored, if appropriate.

If appropriate, a population PK analysis may also be conducted, in addition the plasma concentration-time data may be merged with historical data and analysed as part of a population PK meta-analysis.

